13 APPENDIX II

Amendment Summary of Changes

Amendment 4.0, 14January2022

Protocol Amendment 4 includes the below major changes:

- Updated PVSRIPO to lerapolturev throughout
- Modified lerapolturev dose and dosing schedule
 - Modified other study assessment timepoints impacted by new dosing schedule
 - Added DSMC review once 12 participants have been treated on new dose and schedule (6 to each arm) and clear the DLT period
- Modified the stratification factor of time since prior anti-PD-1/L1 exposure (≤6 weeks versus >6 weeks) to type of anti-PD-1/L1 resistance (primary versus secondary)
- Modified crossover criteria
- Modified study participant inclusion and exclusion criteria as per the below:
 - o Patients with ocular, acral or mucosal melanoma are now excluded
 - Patients with M1c or M1d disease are now excluded
 - Inclusion criterion 5 was modified to clarify definition of resistance to anti-PD-1/L1-based therapy
 - Patients must have not failed more than one prior anti-PD-1/L1-based regimen
- Removed study interim analysis after 20 participants randomized

Amendment 3.0, 23April2021

Protocol Amendment 3 includes the below major changes:

- Added a new primary objective: To evaluate the effect of PVSRIPO on the TME of injected and non-injected lesions when administered with and without anti-PD-1 therapy.
- The primary safety endpoint of "anti-PD-1 AESI" was changed to "anti-PD-1 irAEs" and an irAE definition was added to Section 9.2.
- Modified study participant inclusion and exclusion criteria in Section 4 and the synopsis as per the below:
 - Inclusion criterion 3 was modified to clarify the melanoma subtypes eligible for study participation, requirements for qualifying biopsy and/or archival tissue, and to add the requirement that at least one melanoma lesion is amenable to biopsy while on study.
 - Inclusion criterion 8 no longer includes a minimum serum albumin requirement.
 - Exclusion criterion 1 was added to state exclusion of ocular melanoma
 - Exclusion criteria related to uncontrolled/symptomatic hypercalcemia and worsening steroid myopathy were removed.
 - Added exclusion criterion 20 to clarify that participants unable to interrupt anticoagulant use the day prior, the day of, and the day after each PVSRIPO injection are ineligible for the study.

Confidential Page 107 of 109

- Modified pregnancy testing for women of childbearing potential from approximately every 6 months to approximately every 12 weeks during study participation.
- Clarified the timing of thyroid function monitoring (along with allowable time windows) around were clarified.
- Added mandatory on-study tissue biopsies of injected and non-injected lesions, as well as draining lymph nodes, at multiple timepoints. The types of lesions and conditions under which lesions should be biopsied was clarified throughout.
- Added mandatory blood samples at multiple timepoints on-study. The Day 31 blood sample was removed.
- Updated the Cycle 2 lesion swabbing timepoint from Study Day 24 to Study Day 22 to align with tissue biopsy and blood collection timepoints.
- Clarified tumor imaging requirements throughout the document
- Clarified crossover requirements for participants enrolled in the safety run-in.
- Added clarification to Sections 5.2 and 5.3 to reflect the updated IPHP and device compatibility standards.
- Added clarification in Section 5.4 that COVID vaccination with mRNA-based vaccines is allowed on study, provided the vaccine is administered as far away as possible from injected or injectable melanoma lesions and is given at least 2 weeks before or after PVSRIPO injection.
- Updated Section 5.4 to reflect prohibition of use of steroids with occlusive dressings, warfarin use at any time on study, as well as the use of other anticoagulants the day prior, the day of, or the day after PVSRIPO injection.
- Updated Sections 7.3 and 9.2, along with other areas of the protocol to reflect the requirement to report Grade 3 or 4 ISR within 24 hours of awareness of the event.
- Added Section 8.4.3 to outline the statistical approach to analysis of primary and exploratory translational medicine objectives.

Amendment 2.0, 08November2020

Protocol Amendment 2 includes the below major changes:

- Added additional supporting information regarding the PV booster timing in Section 1.3.1.
- Clarified or modified study participant inclusion and exclusion criteria in Section 4 as per the below:
 - Inclusion criterion 4 modified to require that one melanoma lesion must be injectable and minimal lesion size is 5mm. Clarified that visceral lesions (eg liver, lung, retroperitoneal, subpleural lesions) are not considered injectable for the purposes of this trial.
 - Inclusion criterion 5 modified to require disease progression per iRECIST and added allowance of failure on anti-PD-L1 therapy.
 - Exclusion criterion 13 clarified permissible timeframe for receiving received prior systemic anti-cancer therapy to within 4 weeks or 5 elimination half-lives, whichever is shorter- prior to treatment.

Confidential Page 108 of 109

- For participants crossing over from Arm 1 to Arm 2, added requirement for complete tumor burden assessment (ie, scans or measurements) within 28 days of first treatment in Arm 2 (PVSRIPO/anti-PD-1 combination)
- Clarified that qualifying scans prior to and during screening should be submitted to central imaging vendor, where possible
- Expanded Section 6 to include information on discontinuation of study treatment, treatment beyond progression, and study termination.
- Modified Section 7.2 Safety Assessments timeframe for reporting events to extend reporting periods through 30 days after the last dose of study therapy for AEs and 90 days after the last dose of study therapy or upon resolution/stabilization for AESI and SAEs.
- Added amylase testing to biochemistry laboratory assessments in Section 7.2.2.
- Modified DSMC meeting frequency in Section 9.1.5 to clarify IA meeting and allow for continued regular meetings approximately every 4 months following the IA.

In addition, the study protocol number was modified from PVSRIPO ICI M201 to LUMINOS-102.

Amendment 1.0, 09October2020

The PVSRIPO ICI M201 study protocol Amendment 1 includes the below major changes:

- Addition of a safety run-in of at least 6 subjects receiving single-agent PVSRIPO to characterize safety and tolerability of PVSRIPO when injected into multiple lesions per treatment visit.
- Additional shedding samples to be collected from the PVSRIPO-injected lesions to assess for PVSRIPO poliovirus shedding, in addition to stool shedding testing for PVSRIPO poliovirus.
- Modifying Inclusion Criterion 4 to require at least 2 measurable melanoma lesions according to RECIST 1.1 criteria.
- Modified Inclusion Criterion 6 to specify radiographic confirmation of disease progression on prior anti-PD-1.
- Additional safety monitoring for CRS and ICANS.
- Mandatory blood biopsy samples at screening, prior to study treatment administration at Cycle 3, and upon crossover to Arm 2, where applicable.

In addition, the nomenclature of study visits was updated from "Day" to "Cycle" for clarity and additional clarifications were added to various study visits and procedures to clarify requirements.

Confidential Page 109 of 109

This document describes the statistical methods and data presentations to be used in the planned data summary and analysis of data from Protocol LUMINOS-102. Background information is provided for the overall study design and objectives. The reader is referred to the study protocol and case report forms (CRFs) for details of study conduct and data collection.

1.1. STUDY OVERVIEW

This multi-center, open-label, randomized, Phase 2 study will investigate the efficacy and safety of lerapolturev alone (Arm 1) or in combination with an anti-programmed cell death 1 (PD-1) inhibitor (Arm 2) in participants with unresectable, advanced anti-PD-1/L1 refractory melanoma. Following a 6-participant safety run-in period, up to approximately 50 participants with unresectable cutaneous melanoma who previously failed an anti-PD-1/L1-based therapy will be randomized 1:1 to receive either lerapolturev or lerapolturev plus an anti-PD-1.

As of December 10, 2021, the safety run-in was completed and a total of 17 participants had been enrolled. Upon review of the safety profile for lerapolturev administered as monotherapy or in combination with anti-PD-1 therapy, and in agreement with the Data Safety Monitoring Committee (DSMC), the protocol was amended to allow the total lerapolturev dose to be increased from 6 x 10^8 TCID₅₀/visit to a maximum of 1.6×10^9 TCID₅₀/visit, with up to 6 lesions injected per visit. The lerapolturev dosing schedule (referred to hereafter as once weekly (QW)) was also updated in this amendment to include weekly injections x 7 followed by either dosing every three weeks (Q3W) (lerapolturev monotherapy [Arm 1] or in combination with pembrolizumab [Arm 2]) or dosing every four weeks (Q4W) (combination with nivolumab [Arm 2]).

In Arm 2, anti-PD-1 therapy will be administered per the manufacturer's prescribing information concurrently with lerapolturev beginning Day 1. Participants enrolled in the safety run-in, or those randomized to Arm 1 (lerapolturev only), are allowed to crossover to Arm 2 for the following reasons: (1) disease progression per Response Evaluation Criteria in Solid Tumors (RECIST) 1.1, (2) once a partial response (PR) lasts at least 6 months, (3) after 26 weeks on study without RECIST-defined progression (ie, stable disease (SD) or unconfirmed PR or complete response (CR)). Those participants who crossover to Arm 2 may be required to repeat or continue the QW dosing, depending on when the crossover occurs, as shown in Table 1 (See Section 3.1.1 of the Study Protocol for additional information).

Table 1. Lerapolturev Injection Schedule After Crossover

Schedule of lerapolturev monotherapy injections at the time of crossover	Timing of when criteria for crossover are met	Recommended lerapolturev dosing schedule for combination
Participant is receiving weekly injections	< 6 months from Cycle 1 Day 1	Continue QW injections for a total of 7 (monotherapy + combination) followed by Q3W dosing (pembrolizumab) or Q4W dosing (nivolumab)*
Participant is receiving injections Q3W (pembrolizumab) or Q4W (nivolumab)	< 6 months from Cycle 1 Day 1	Continue concurrent dosing schedule

Schedule of lerapolturev monotherapy injections at the time of crossover	Timing of when criteria for crossover are met	Recommended lerapolturev dosing schedule for combination
Participant is receiving injections Q3W (pembrolizumab) or Q4W (nivolumab)	≥ 6 months from Cycle 1 Day 1	Weekly x 7 followed by every Q3W (pembrolizumab) or Q4W dosing (nivolumab)

After 12 participants have been treated under Study Protocol Amendment 4 (amendment that increased the lerapolturev dose and changed to QW injection schedule) and on study approximately 21 days (ie, once n=6 participants per treatment arm receiving lerapolturev QW have completed the dose-limiting toxicity (DLT) evaluation period), an additional safety review will be performed by the DSMC to confirm the safety of lerapolturev with or without anti-PD-1 and/or to make recommendations related to lerapolturev dose and/or schedule adjustments.

Participants receiving the Q3/4W schedule of injections are required to receive the increased lerapolturev dose and will be given the option to change to the QW schedule once Study Protocol Amendment 4 is open at their respective site.

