1.2.2.2 Lerapolturev in patients with melanoma

Lerapolturev has been administered via intratumoral injection (1 x 10⁸ TCID₅₀ per lesion per visit) to 12 participants in a Phase 1 open-label study with unresectable and/or metastatic anti-PD-1 refractory melanoma (as defined by the investigator) as of 23 March 2021 (NCT03712358). No serious adverse events (SAEs) or dose-limiting toxicities (DLTs) were observed, and administration of 1 x 10⁸ TCID₅₀ lerapolturev to one lesion/visit

Confidential Page 37 of 109

for up to three successive visits was well tolerated. This included 5 participants that received 3 injections of lerapolturev who had received prior anti-PD-1 therapy within 30 days prior to administration of lerapolturev (and thus had anti-PD1 therapy on board during lerapolturev); none of these participants experienced systemic toxicities. All AEs were Grade 1 or 2 in severity (pruritis [58%] and erythema [50%]) and primarily localized to the injected lesion(s).

Based on the favorable tolerability profile, and encouraging preliminary anti-tumor activity (33% ORR per irRC) noted in Phase 1, this study (NCT04577807) was designed to test the safety and efficacy of lerapolturev alone or in combination with anti-PD-1 therapy, in participants with unresectable melanoma who meet the more rigorous and objective definition for anti-PD-1 resistance, as described in the SITC Immunotherapy Resistance Task Force Guidance⁷. Despite a 6-fold increase in the total maximum lerapolturev dose relative to Phase 1 (ie, 6 x 10⁸ TCID₅₀ versus 1 x 10⁸ TCID₅₀ in Phase 1) and/or injection of up to 6 lesions per treatment visit (compared to 1 lesion/visit in Phase 1), lerapolturev remains well tolerated, whether given alone or when combined with anti-PD-1 therapy. As summarized in Table 3 and Table 4, 17 participants were treated with lerapolturev monotherapy (n=11) or lerapolturev combined with anti-PD-1 therapy (n=6) as of the 10 December 2021 data cutoff. Additionally, 7 lerapolturev monotherapy participants crossed over to receive the lerapolturev/anti-PD-1 combination.

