8.6 Interim Analysis (IA)

No interim analysis will be conducted for this study. Rather, efficacy results for participants receiving the **Q3/4W** schedule and **QW** schedule will be summarized separately for participants receiving either lerapolturev monotherapy or lerapolturev in combination with anti-PD-1 therapy, as described in the SAP.

Confidential Page 83 of 109

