5. STATISTICAL METHODS

Descriptive statistical methods will be used to summarize the data from this study. Unless stated otherwise, the term "descriptive statistics" refers to number of participants (n), mean, median, standard deviation, minimum and maximum for continuous data and frequencies and percentages for categorical data.

Survival endpoints will be analyzed with Kaplan-Meier method and summarized with median, twenty-fifth and seventy-fifth percentiles, and 95% confidence intervals (CI), if applicable.

All data collected during the study will be included in data listings. Unless otherwise noted, the data will be sorted first by treatment, participant, and then by date within each participant number.

All summary tables and figures will be presented by treatment group and overall. The term "treatment group" refers to the following subgroups:

- lerapolturev monotherapy on the QW schedule
- lerapolturev monotherapy on the Q3/4W schedule
- lerapolturev + anti-PD-1 on the QW schedule
- lerapolturev + anti-PD-1 on the Q3/4W schedule
- all crossover to lerapolturev + anti-PD-1 participants
- lerapolturev + anti-PD-1 plus crossover participants (all lerapolturev + anti-PD-1)
- overall treated participants

Analyses will be implemented using SAS® 9.4 or higher (SAS Institute, Cary, North Carolina, USA). The International Conference on Harmonization (ICH) numbering convention (ie, ICH-E3) will be used for all tables and listings. Upon completion, all SAS® programs will be validated by an independent programmer within the staff of the third-party vendor doing the primary analysis. The validation process will be used to confirm that statistically valid methods have been implemented and that all data transformations and calculations are accurate. Checks will be made to ensure accuracy, consistency with this plan, consistency within tables, and consistency between tables and corresponding data listings. All documents will be verified by the lead statistician to ensure accuracy and consistency of analyses.

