5.6.1.1. Statement of Estimand

The **population for the trial** is defined through appropriate inclusion/exclusion criteria to reflect the targeted participant population for approval. The analysis population is based on the efficacy population.

The **treatments** of interest are lerapolturev alone or lerapolturev + an FDA-approved anti-PD-1 therapy by dosing schedule.

The **variable** of interest for ORR is the binary response value for a participant.

The ability to evaluate treatment effect using the variables may be impacted by **intercurrent events** (ICEs). Death and use of additional cancer treatments may all impact the interpretation of treatment effect. For ORR, a composite strategy will be used to address intercurrent events (ICEs) of potential death, and start of additional cancer treatments, meaning occurrence of any of these events prior to a participant achieving CR or PR will mean the participant is considered a non-responder.

The **population level summary measures** are the ORR and associated confidence intervals in each treatment arm and lerapolturev dosing schedule.

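### The SAP reports all crossover participants in one column that spans two dose levels, several injection schedules and opposite reasons for crossing, although results are meant to be shown by dosing schedule

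*SAP*

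**What the plan says.** **Who crosses and what follows.** SAP 1.1 allows crossover for three reasons. The first two are "1) disease progression per Response Evaluation Criteria in Solid Tumors (RECIST) 1.1, (2) once a partial response (PR) lasts at least 6 months"; the third is 26 weeks on study without progression. It adds: "Those participants who crossover to Arm 2 may be required to repeat or continue the QW dosing, depending on when the crossover occurs". SAP Table 1 gives three post-crossover schedules:

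- still on weekly injections, before 6 months: complete the series to 7 in total, counting those given as monotherapy;
- on maintenance, before 6 months: "Continue concurrent dosing schedule", so no weekly injections;
- on maintenance, at 6 months or later: weekly x 7.

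**Dose.** SAP 1.1 records that the per-visit maximum rose from 6 x 10^8 to 1.6 x 10^9 TCID50 under the amendment, which Protocol Appendix II dates 14 January 2022. Protocol 1.2.2.2 records that by the 10 December 2021 cutoff "7 lerapolturev monotherapy participants crossed over to receive the lerapolturev/anti-PD-1 combination".

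**Reporting groups.** SAP 3.2.1 and 5 list seven. Monotherapy and combination are each divided into QW and Q3/4W. Crossovers appear as "all crossover to lerapolturev + anti-PD-1 participants" and again in "lerapolturev + anti-PD-1 plus crossover participants (all lerapolturev + anti-PD-1", neither divided.

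**What is promised by schedule.** Protocol 8.6 says that efficacy results for the two schedules "will be summarized separately for participants receiving either lerapolturev monotherapy or lerapolturev in combination" with anti-PD-1. The SAP 5.6.1.1 summary measure is "the ORR and associated confidence intervals in each treatment arm and lerapolturev dosing schedule", and SAP 5.6.1.2 computes ORR by treatment group and dosing schedule. No section says to which schedule a crossover participant belongs.

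**Is the analysis kept?** SAP 7 lists the crossover subgroup among the ORR, DOR, DRR, DCR, OS and PFS analyses no longer conducted. SAP 3.2.6 still includes crossovers in the OS and PFS analyses, and SAP 5 applies its seven groups to all summary tables and figures.

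**The concern.** The sponsor raised the dose and intensified the schedule because the best response on Q3/4W had been stable disease (Protocol 1.2.2.2). Keeping QW and Q3/4W apart is therefore the point of the reporting structure. The crossover column ignores that divide, in a group whose early members are known to have crossed under the old regimen.

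It also averages over prognosis. Participants who cross after progression start from a grown tumour. Those who cross in lasting partial response, or without progression at 26 weeks, start from a shrunken or stable one. Response after crossover is measured from tumour size at crossover (Protocol 8.5.4), so one ORR combines unlike starting points.

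The Protocol synopsis makes response on anti-PD-1 re-challenge an efficacy criterion, analysed from crossover and separately from Arm 2. A reader of the clinical study report will look to this column for evidence on that question and could take it as the result of the current regimen. The safety column has the same problem, since it combines exposure under two per-visit maxima.

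**Working it through.** **1. The plan's own figure.** The only design precision stated is for Arm 2 QW: 5 of 15 responders. The Clopper-Pearson 95% limits are the 2.5% quantile of Beta(x, n-x+1) and the 97.5% quantile of Beta(x+1, n-x). For x = 5, n = 15 they are 11.8% and 61.6%, as stated. For 4/15 the lower limit is 7.8%, so 5 is the minimum number of responses. No size or precision is stated for the crossover group.

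**2. Dose mix.** Ratio of per-visit maxima: 16 x 10^8 / 6 x 10^8 = 2.67. The 7 known crossovers precede Amendment 4, so they crossed on Q3/4W under the lower maximum. SAP 1.1 then requires Q3/4W participants still on treatment to take the increased dose, and lets them switch to QW, once the amendment opens at their site. Dose therefore follows Amendment 4, while Table 1 governs schedule.

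**3. How reason and schedule line up.**
- Weekly injections 1 to 7 fall on days 1, 8, 15, 22, 29, 36 and 43. The week-6 scan falls on day 1 + 42 = 43. A participant dosed on time who progresses at the first scheduled scan has reached the seventh injection, so the completing-the-series row should be sparse.
- A partial response lasting 6 months puts crossover at 6 months or later. Week 26 is 182 days, against 182.6 days for half a year. Crossing without progression therefore falls essentially in the weekly x 7 row.
- Only progression can fall in all three rows. Schedule is thus tied to prognosis, and cross-tabulating both would largely duplicate information.

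**4. Size of the dilution (assumed counts).** The final crossover number is not stated. It is at least 7, with an assumed ceiling of 31 (6 run-in plus about 25 in Arm 1). Suppose 10 later crossovers, and that the 7 early ones never respond. Whatever the number of responses r, the pooled ORR is 10/17 = 59% of the later crossovers' ORR:

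| Responses r | Later only, r/10 (lower 95% limit) | Pooled, r/17 (lower 95% limit) |
|---|---|---|
| 3 | 30% (6.7%) | 17.6% (3.8%) |
| 4 | 40% (12.2%) | 23.5% (6.8%) |
| 5 | 50% (18.7%) | 29.4% (10.3%) |

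The upper limits at r = 4 are 73.8% and 49.9%. Over r = 0 to 10, pooling moves the lower limit across 10% only at r = 4.

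**5. Dependence on the mix (assumed rates).** Take true ORRs of 5%, 20% and 40% for no weekly injections, completing the first series, and weekly x 7. A 60/10/30 mix gives 0.6 x 5 + 0.1 x 20 + 0.3 x 40 = 17.0%. A 30/10/60 mix gives 0.3 x 5 + 0.1 x 20 + 0.6 x 40 = 27.5%. The column moves by 10.5 points with no change in effect within any route.

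**6. Precision after a split.** At about one-third response: 3/10 gives 6.7% to 65.2%, 2/7 gives 3.7% to 71.0%, and 1/3 gives 0.8% to 90.6%. Two columns are workable. Finer cells support counts only.

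**The case against.** The SAP follows the protocol's own grouping. Protocol 8.4 defines a single Crossover population, 8.5.4 summarises it separately, and Protocol Tables 3 and 4 already pool crossovers. All analyses are descriptive, crossover subgroup outcomes are exploratory in the protocol, and the activity criterion concerns Arm 2 QW only. SAP 5.6.1.2 already asks for ORR by dosing schedule within treatment group, SAP 5.7.1 permits further adverse event analyses by dose or schedule, SAP 5.5 summarises TCID50 per cycle, and injections and responses are listed by participant. Cells will be small, and an early-crossover column is not a clean regimen because its members may have moved to the new dose or to QW.

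Most of this stands, and it limits the point. It does not remove it. The by-schedule instruction cannot be programmed for crossovers without an assignment rule, the safety analyses are optional, and listings leave the reader to rebuild the split. Small cells argue for counts, not for pooling across a regimen change.

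Four stronger readings are tempting but unsupported:

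- *The column describes nothing.* It does describe adding anti-PD-1 after lerapolturev monotherapy under the crossover rules; it does not describe one dose or schedule.
- *Some crossovers get a partial second induction.* The relevant row of Table 1 completes the first series, and for someone never dosed weekly, weekly x 7 is a first induction.
- *Pooling could overturn the activity conclusion.* The 10% benchmark is never applied to crossovers, and the lower limit crosses it at only one assumed count.
- *The Arm 2 QW result is contaminated.* The SAP lists that group apart from the group that adds crossovers. Its rule of analysing by treatment at the time of assessment (SAP 4.2) makes it worth saying so explicitly.

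**Conclusion.** The gap is real and modest. The crossover column combines at least 7 participants who crossed on Q3/4W under a 6 x 10^8 maximum with later crossovers under a 1.6 x 10^9 maximum and one of three schedules, and it combines progressors with non-progressors. Its ORR, OS, PFS and safety figures cannot be attributed to a single dose or schedule, although the SAP separates schedules in its four non-crossover groups.

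No trial decision changes. The size is uncertain because neither the number of later crossovers nor any response count is given. The fall from 40% to 23.5% rests on assumed counts of 10 and 4 and on no response among the first 7; it illustrates dilution and predicts nothing. What comes first is that SAP 7 and SAP 3.2.6 and 5 disagree on whether crossover efficacy is reported at all. The change is worthwhile because it is cheap.

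**What to change.** 1. Reconcile SAP 7 with SAP 3.2.6 and 5: state which crossover efficacy analyses are kept.
2. Where crossover results are reported, replace the all-crossover column in SAP 3.2.1 and 5, and the matching OS and PFS subgroups in 3.2.6, with two columns assigned by crossover date: before Amendment 4, and under it. Define the boundary (for example, the date the amendment opened at the participant's site) and use it for the by-schedule results in 5.6.1.2.
3. Flag participants in the first column who later moved to the new dose or to QW.
4. Show crossovers by reason (RECIST progression versus no progression) as counts, and put the post-crossover schedule in the listing.
5. Keep the Arm 2 columns free of crossovers, in line with the protocol's rule of separate analysis.
6. Reconcile the third crossover reason, since it defines the non-progressor group: footnote 13 of SAP Table 2 says 36 weeks, while SAP 1.1, SAP Table 3 and the protocol say 26.

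**Cost:** SAP wording and a few columns and rows, drawing on injection and response data already planned for listing. The documents do not show that the reason for crossing is captured directly; if it is not, it can be derived from RECIST assessments and dates. The downside is small cells with wide intervals, so counts should lead.
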